## 12.8 Sample size calculation

### 12.8.1 Primary endpoint(s)

The planned total sample size in this proposed China-centric phase 3 study is 550 subjects. The key assumptions in calculating the sample size are based on prior results from erenumab global pivotal study. A treatment difference in terms of change from baseline on MMDs during Week 9-12 (primary endpoint) for erenumab 70 mg vs. placebo is assumed at -2.0 days. The common standard deviation of the primary variable is assumed at 6.8. Given a 1:1 randomization ratio among erenumab 70 mg and placebo, it requires a total of 550 subjects (including 10% drop out rate) to achieve approximate 90% power to demonstrate the treatment difference of erenumab 70 mg compared with placebo under two-sided 0.05 alpha level. The impact of spending alpha at unblinded interim analysis on sample size and power is relatively negligible. Having this interim analysis with alpha spending at 0.014 two-sided, at final analysis an observed p-value

$\leq 0.046$  two-sided would be required (given that the interim analysis was performed when 70% subject finished treatment or early withdraw). With that said, the overall power will be maintained approximately at 90% with planned sample size.

The sample size for Chinese sub-population will make sure the consistency of treatment effect between Chinese and total population. The methods for consistency assessment is proposed as,

$$\Pr(D_{\text{China}} / D_{\text{Overall}} > 0.5) > 95\%,$$

which means that this China study should have high probability ( $>95\%$ ) to demonstrate consistency where the treatment effect (treatment difference of erenumab compared with placebo) observed in the Chinese population should be as high as at least 50% of the treatment effect observed in the overall study population in the prospective trial, assuming there is no difference between the Chinese population assessed in the trial and the overall population.

To meet the above criteria, approximately 350 (out of 550 for the overall study) Chinese subjects will be recruited.

At the interim analysis, as long as China population takes the majority of the overall population, there should have high likelihood to demonstrate the consistency as well.

## **13 Ethical considerations and administrative procedures**

### **13.1 Regulatory and ethical compliance**

This clinical study was designed and shall be implemented, executed and reported in accordance with the ICH Harmonized Tripartite Guidelines for Good Clinical Practice, with applicable local regulations (including European Directive 2001/20/EC, US CFR 21), and with the ethical principles laid down in the Declaration of Helsinki.

### **13.2 Responsibilities of the investigator and IRB/IEC**

Before initiating a trial, the investigator/institution must obtain approval/favorable opinion from the Institutional Review Board/Independent Ethics Committee (IRB/IEC) for the trial protocol, written informed consent form, consent form updates, subject recruitment procedures (e.g., advertisements) and any other written information to be provided to subjects. Prior to study start, the investigator is required to sign a protocol signature page confirming his/her agreement to conduct the study in accordance with these documents and all of the instructions and procedures found in this protocol and to give access to all relevant data and records to Novartis monitors, auditors, Novartis Quality Assurance representatives, designated agents of Novartis, IRBs/IECs, and regulatory authorities as required. If an inspection of the clinical site is requested by a regulatory authority, the investigator must inform Novartis immediately that this request has been made.

As mentioned in Section 7, during the COVID-19 pandemic, the training related to the home-delivery of study drug should be documented in the subject chart.

### **13.3 Publication of study protocol and results**

The protocol will be registered in a publicly accessible database such as clinicaltrials.gov and as required in EudraCT. In addition, after study completion (defined as last patient last visit)

and finalization of the study report the results of this trial will be submitted for publication and posted in a publicly accessible database of clinical trial results, such as the Novartis clinical trial results website and all required Health Authority websites (e.g. Clinicaltrials.gov, EudraCT etc.).

For details on the Novartis publication policy including authorship criteria, please refer to the Novartis publication policy training materials that were provided to you at the trial investigator meetings.

### **13.4 Quality Control and Quality Assurance**

Novartis maintains a robust Quality Management System (QMS) that includes all activities involved in quality assurance and quality control, to ensure compliance with written Standard Operating Procedures as well as applicable global/local GCP regulations and ICH Guidelines.

Audits of investigator sites, vendors, and Novartis systems are performed by auditors, independent from those involved in conducting, monitoring or performing quality control of the clinical trial. The clinical audit process uses a knowledge/risk-based approach.

Audits are conducted to assess GCP compliance with global and local regulatory requirements, protocols and internal Standard Operating Procedures (SOPs), and are performed according to written Novartis processes.

## **14 Protocol adherence**

This protocol defines the study objectives, the study procedures and the data to be collected on study participants. Additional assessments required to ensure safety of subjects should be administered as deemed necessary on a case by case basis. Under no circumstances including incidental collection is an investigator allowed to collect additional data or conduct any additional procedures for any purpose involving any investigational drugs under the protocol, other than the purpose of the study. If despite this interdiction prohibition, data, information, observation would be incidentally collected, the investigator shall immediately disclose it to Novartis and not use it for any purpose other than the study, except for the appropriate monitoring on study participants.

Investigators ascertain they will apply due diligence to avoid protocol deviations. If an investigator feels a protocol deviation would improve the conduct of the study this must be considered a protocol amendment, and unless such an amendment is agreed upon by Novartis and approved by the IRB/IEC and health authorities, where required, it cannot be implemented.

### **14.1 Protocol Amendments**

Any change or addition to the protocol can only be made in a written protocol amendment that must be approved by Novartis, health authorities where required, and the IRB/IEC prior to implementation.

Only amendments that are required for subject safety may be implemented immediately provided the health authorities are subsequently notified by protocol amendment and the reviewing IRB/IEC is notified.

Notwithstanding the need for approval of formal protocol amendments, the investigator is expected to take any immediate action required for the safety of any subject included in this study, even if this action represents a deviation from the protocol. In such cases, Novartis should be notified of this action and the IRB/IEC at the study site should be informed according to local regulations.

## 16 Appendices

### 16.1 Appendix 1: Clinically notable laboratory values and vital signs

Only selected lab parameters which have potential to be sensitive to erenumab exposure are listed.

**Table 16-1 Clinically notable laboratory values**

Laboratory Variable	Gender (M/F/Both)	Standard Units	SI Units
LIVER FUNCTION AND RELATED VARIABLES			
SGOT (AST)	F	>93 U/L	>93 U/L
SGOT (AST)	M	>111 U/L	>111 U/L
SGPT (ALT)	F	>90 U/L	>90 U/L
SGPT (ALT)	M	>123 U/L	>123 U/L
Total bilirubin	Both	>3.6 mg/dL	>63 mmol/L
Alkaline Phosphatase	F	>832 U/L	>832 U/L
Alkaline Phosphatase	M	>1032 U/L	>1032 U/L
HEMATOLOGY VARIABLES			
Neutrophils	Both	<1.5 x 10  /uL	<1.5 x10  /L

## 16.2 Appendix 2: Liver event and Laboratory trigger Definitions and Follow-up Requirements

**Table 16-2 Liver Event and Laboratory Trigger Definitions**

	Definition/ threshold
LIVER LABORATORY TRIGGERS	
 
• <math>3 \times \text{ULN} < \text{ALT} / \text{AST} \leq 5 \times \text{ULN}</math>
 
• <math>1.5 \times \text{ULN} < \text{TBIL} \leq 2 \times \text{ULN}</math>
 

LIVER EVENTS	
 
• <math>\text{ALT or AST} > 5 \times \text{ULN}</math>
 
• <math>\text{ALP} > 2 \times \text{ULN}</math> (in the absence of known bone pathology)
 
• <math>\text{TBIL} > 2 \times \text{ULN}</math> (in the absence of known Gilbert syndrome)
 
• <math>\text{ALT or AST} > 3 \times \text{ULN}</math> and <math>\text{INR} > 1.5</math>
 
• Potential Hy's Law cases (defined as <math>\text{ALT or AST} > 3 \times \text{ULN}</math> and <math>\text{TBIL} > 2 \times \text{ULN}</math> [mainly conjugated fraction] without notable increase in ALP to <math>> 2 \times \text{ULN}</math>)
 
• Any clinical event of jaundice (or equivalent term)
 
• <math>\text{ALT or AST} > 3 \times \text{ULN}</math> accompanied by (general) malaise, fatigue, abdominal pain, nausea, or vomiting, or rash with eosinophilia
 
• Any adverse event potentially indicative of a liver toxicity*
 

\*These events cover the following: hepatic failure, fibrosis and cirrhosis, and other liver damage-related conditions; the non-infectious hepatitis; the benign, malignant and unspecified liver neoplasms TBIL: total bilirubin; ULN: upper limit of normal

**Table 16-3 Follow Up Requirements for Liver Events and Laboratory Triggers**

Criteria	Actions required	Follow-up monitoring
Potential Hy's Law case a	
 
• Discontinue the study treatment immediately
 
• Hospitalize, if clinically appropriate
 
• Establish causality
 
	ALT, AST, TBIL, Albumin, PT/INR, ALP and GGT until resolution c (frequency at investigator discretion)
ALT or AST		
$> 8 \times \text{ULN}$	
 
• Discontinue the study treatment immediately
 
• Hospitalize if clinically appropriate
 
• Establish causality
 
	ALT, AST, TBIL, Albumin, PT/INR, ALP and GGT until resolution c (frequency at investigator discretion)
$> 3 \times \text{ULN}$ and $\text{INR} > 1.5$	
 
• Discontinue the study treatment immediately
 
	ALT, AST, TBIL, Albumin, PT/INR, ALP and GGT until resolution c (frequency at investigator discretion)

Criteria	Actions required	Follow-up monitoring
> 5 to $\leq$ 8 $\times$ ULN	

• Hospitalize, if clinically appropriate

• Establish causality

• Repeat LFT within 48 hours

• If elevation persists, continue follow-up monitoring

• If elevation persists for more than 2 weeks, discontinue the study drug

• Establish causality

	ALT, AST, TBIL, Albumin, PT/INR, ALP and GGT until resolution c (frequency at investigator discretion)
> 3 $\times$ ULN accompanied by symptoms b	

• Discontinue the study treatment immediately

• Hospitalize if clinically appropriate

• Establish causality

• Complete liver CRF

	ALT, AST, TBIL, Albumin, PT/INR, ALP and GGT until resolution c (frequency at investigator discretion)
> 3 to $\leq$ 5 $\times$ ULN (subject is asymptomatic)	

• Repeat LFT within the next week

• If elevation is confirmed, initiate close observation of the subject

	Investigator discretion Monitor LFT within 1 to 4 weeks
ALP (isolated)		
> 2 $\times$ ULN (in the absence of known bone pathology)	

• Repeat LFT within 48 hours

• If elevation persists, establish causality

	Investigator discretion Monitor LFT within 1 to 4 weeks or at next visit
TBIL (isolated)		
> 2 $\times$ ULN (in the absence of known Gilbert syndrome)	

• Repeat LFT within 48 hours

• If elevation persists, discontinue the study drug immediately

• Hospitalize if clinically appropriate

• Establish causality

	ALT, AST, TBIL, Albumin, PT/INR, ALP and GGT until resolution c (frequency at investigator discretion) Test for hemolysis (e.g. reticulocytes, haptoglobin, unconjugated [indirect] bilirubin)
> 1.5 to $\leq$ 2 $\times$ ULN (subject is asymptomatic)	

• Repeat LFT within the next week

• If elevation is confirmed, initiate close observation of the subject

	Investigator discretion Monitor LFT within 1 to 4 weeks or at next visit
Jaundice	

• Discontinue the study treatment immediately

	ALT, AST, TBIL, Albumin, PT/INR, ALP and GGT until

Criteria	Actions required	Follow-up monitoring
Any AE potentially indicative of a liver toxicity*	

• Hospitalize the subject

• Establish causality

• Consider study treatment interruption or discontinuation

• Hospitalization if clinically appropriate

• Establish causality

	resolution c (frequency at investigator discretion) Investigator discretion

aElevated ALT/AST > 3 × ULN and TBIL > 2 × ULN but without notable increase in ALP to > 2 × ULN

b(General) malaise, fatigue, abdominal pain, nausea, or vomiting, or rash with eosinophilia

cResolution is defined as an outcome of one of the following: (1) return to baseline values, (2) stable values at three subsequent monitoring visits at least 2 weeks apart, (3) remain at elevated level after a maximum of 6 months, (4) liver transplantation, and (5) death.

MAR	Missing at Random
MCMC	Markov Chain Monte Carlo
MedDRA	Medical Dictionary for Drug Regulatory Affairs
MI	Multiple Imputation
MIN	Minimum function
mMIDAS	Modified Migraine Disability Assessment
MNAR	Missing Not at Random
NRI	Non-Responder Imputation
OLE	Open-label extension
PD	Protocol Deviations

PRO	Subject-Reported Outcomes
PT	Preferred Term
qm	once a month
SAE	Serious Adverse Event
SAF	SAFety analysis set
SAP	Statistical Analysis Plan
sc	Subcutaneous
SD	Standard Deviation
SOC	System Organ Class
SSAP	Supplemental Statistical Analysis Plan
TEAE	Treatment-Emergent Adverse Event
TFLs	Tables, Figures, Listings
ULN	Upper Limit of Normal
UN	Unstructured covariance matrix
US	United States
VAS	Visual Analog Scale
VS	Vital Signs
WHO	World Health Organization

1 Introduction

The purpose of this statistical analysis plan (SAP) is to provide details of the statistical analysis according to Section 12 of the study protocol (**v02**) for AMG 334 Study CAMG334A2304 dated 26 Jan 2021 and along with any additional analyses, specifications or deviations from the protocol planned.

The scope of this plan includes the primary, secondary, [REDACTED] analyses, which will be executed by Novartis internal statisticians and programmers, if not specified differently. Those analyses will be reported in the CSR.

1.1 Study design

This study uses a single-cohort, 2-treatment arm, randomized (1:1 [70 mg: placebo]), double-blind study design in adult subjects with chronic migraine (see Figure 1-1).

The following periods are included in the study design:

- Screening period of 2 weeks: to assess initial eligibility,
- Baseline period of 4 weeks: All subjects successfully completing the Screening period are invited to participate. Final eligibility prior to randomization and dosing will be assessed based on headache frequency and diary compliance during this period,
- Double-blind treatment (DB) period of 12 weeks: All subjects successfully completing the Baseline period are invited to participate. Eligible subjects will be randomized to one of two treatment arms. At the end of this period, the final assessment to address the efficacy-related objectives will occur.
- Post double-blind treatment follow-up of 12 weeks: for subjects discontinuing treatment during the double-blind treatment period and willing to return for the subsequent scheduled follow-up (FUP) visits, until the Week 12 follow-up visit.
- Safety follow-up period of 8 weeks: a Safety Follow-Up visit, will occur 8 weeks after the 12 weeks' DB, at Week 20 for subjects who complete the double-blind treatment period (including complete post treatment follow-up visits) but not enter into the open-label treatment period. For subjects who discontinue double-blinded period (NOT willing to return for scheduled visits until week 12), they will be suggest to complete safety follow-up visit 12 weeks after the last dose.
- Open-label treatment extension (OLE) period (until launch of erenumab in the country or until June 2021 in Korea): all subjects completing the double-blind treatment period on study drug are invited to participate. Eligible subjects who consent to participate in this open-label treatment period will receive erenumab until it is launched in the country or until June 2021 in Korea, in order to ensure continued drug access.

End of Trial (Last Subject Last Visit, LPLV) will occur when all subjects have completed their last visit.

[figure not shown]
Approximatively 550 subjects will be randomized (275 in placebo, 275 in AMG334 70mg), stratified by prior prophylactic migraine medication treatment failure (prior prophylactic

migraine treatment failure due to efficacy or tolerability vs. no prior prophylactic migraine treatment failure) and medication overuse (yes vs. no).

Two interim analyses (IA) are planned for this study.

- A blinded IA, after approximately 50% (275) of subjects have completed the double-blind treatment period (including early withdrawals), will be conducted to re-estimate the sample size.
- An unblinded IA will be conducted at the time of 70% (385, based on the currently planned sample size 550 if no need for sample size increase after the blinded IA) of subjects have completed the double-blind treatment period (including early withdrawals), to determine whether the study will stop early or continue to the final primary analysis (full sample size).

Figure 1-1 Study Design Schematic

[figure not shown]
Note: For subjects not entering the Open-Label Treatment period, Safety Follow-Up visit will occur 8 weeks after last visit of the Double-Blind Treatment period

1.2 Study objectives and endpoints

Table 1-1 Objectives and related endpoints

Objective(s)	Endpoint(s)
Primary objective(s)	Endpoint(s) for primary objective(s)

• To evaluate the effect of erenumab compared to placebo on the change from baseline in monthly migraine days, in subjects with chronic migraine	
• Change from baseline in monthly migraine days during the last 4 weeks of the 12-week treatment period
Secondary objective(s)	Endpoint(s) for secondary objective(s)

• To evaluate the effect of erenumab compared to placebo on change from baseline in migraine-related disability and productivity as measured by the modified Migraine Disability Assessment (mMIDAS)	
• Change from baseline in migraine-related disability and productivity as measured by the mMIDAS during the last 4 weeks of the 12-week treatment period

Objective(s)	Endpoint(s)

• To evaluate the effect of erenumab compared to placebo on the proportion of subjects with at least 50% reduction from baseline in monthly migraine days• To evaluate the effect of erenumab compared to placebo on the change from baseline in monthly acute headache medication days• To evaluate the safety and tolerability of erenumab	
• Achievement of at least a 50% reduction from baseline in monthly migraine days during the last 4 weeks of the 12-week treatment period• Change from baseline in monthly acute headache medication days during the last 4 weeks of the 12-week treatment period• Adverse events, clinical laboratory values, vital signs, and anti-AMG 334 antibodies

2 Statistical methods

2.1 Data analysis general information

Data from the study will be analyzed based on the study phase as defined in Table 2-1. The full scope of data analysis defined in this document is pertinent to both DB period (including safety follow-up), and OLE period. The sub-scope of data analysis for the unblinded interim readout is defined in section 2.12.

Table 2-1 Study Phases for data analysis

Study Phase	Start Time Point	End Time Point
DB Period (including Safety follow-up)	Study Day 1 (after the 1st DB IP Dose)	For subject who won't join in OLE: end of study date; For subject who join in OLE: the End of Treatment visit in DB period (the last visit scheduled in DB Period)
OLE Period (applicable for subjects continuing OLE treatment)	The End of Treatment Visit in DB Period + 1	For subject who join in OLE: end of study date

*In general, if the End of Treatment visit date of DB period and the 1st OLE IP injection are on the same day, then the AE or CM which occurs on that day will be considered to belong to DB

period. [REDACTED]

In the case of a positive unblinded IA read-out (success), an interim CSR based on the 70% subjects (DB period completers or early withdrawers up to the unblinded IA cutoff) who are included in the unblinded IA analysis will be generated. The primary analysis will be performed for DB period. Ongoing DB period subjects at the time of unblinded IA cutoff will not be included in this interim CSR. Their data will be reported in an addendum for the interim CSR, when all subjects completed their last visit in DB period. In this interim CSR addendum, those ongoing subjects together with the 70% subjects who have been included in the interim CSR, will be analyzed again and data will be mainly presented by summary statistics. The interim CSR and its addendum will be prepared for regulatory submission.

In case the trial needs to continue enrollment to full sample size as all enrolled subjects have completed DB period, the primary database lock will then be performed. One interim CSR based on all data from DB period and safety follow up collected up to the cutoff timepoint for the primary lock will be prepared for regulatory submission.

At the end of OLE period, a final CSR for data from OLE will be prepared supplementally.

Unless otherwise stated, summary tables/listings/figures will be presented for each treatment arm in the respective analysis set. In general data of interest will be listed by treatment arm and by country name/center number/subject id (/visit wherever applicable). For OLE period, data will be displayed by the treatment arm as in DB period as well as overall.

Categorical data will be presented as frequencies and percentages. For continuous data, the number of non-missing observations, mean, standard deviation (SD), median, minimum and maximum will be presented. Summary tables will also be presented by visit wherever applicable.

For efficacy endpoints, graphs will display results where it is appropriate.

General information on treatment arm handling, decimal places and other output-related information will be specified in tables, figures and listing (TFLs) shells accompanying this analysis plan.

Randomization will be stratified by prior prophylactic migraine medication treatment failure (yes vs. no) and medication overuse (yes vs. no). Stratification factors used as covariates in the analysis will use the values used for randomization unless otherwise noted.

Statistical analysis of all data will be performed using SAS® statistical software (SAS Institute, Cary, NC, USA.) version 9.4 or higher.

The full scope of analysis described below will be performed by Novartis. The unblinded IA read-out will be performed by the independent statistical analysis team outside Novartis, for the requirement of Data Monitoring Committee (DMC) meeting. The process in details are defined in DMC Charter.

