- **Safety follow-up (8 weeks):** in subjects completing the double-blind treatment period, but not entering into the open-label treatment period, a safety follow-up visit will occur 8 weeks after the Week 12 visit (Week 20). Subjects who discontinue study drug during the double-blind treatment period and who do not remain in the study to follow the assessment schedule until the Week 12 FUP visit, will have the safety follow-up visit 12 weeks after the last dose. For subjects discontinuing double-blind treatment and remaining in the study to follow the assessment schedule until the Week 12 FUP visit, the Safety Follow-Up visit should occur on Week 20 even if the last dose was taken at Day 1. The Safety Follow-Up visit is not required in subjects who discontinue or complete the open-label treatment period.
- **Open-label treatment (until launch of erenumab in the country or until June 2021 in Korea):** all subjects completing the double-blind treatment period on study drug are invited to participate. Eligible subjects who consented to participate in this open-label treatment period will receive erenumab until it is launched in the country, or until June 2021 in Korea, in order to ensure continued drug access.

Should a treatment gap exist between the two treatment periods due to a delay of HA/EC approvals or other administrative/logistical reasons, the subject may enter the open-label treatment period at a later time provided he or she still meets the eligibility criteria. During this treatment gap, the subject is allowed to use standard of care.

See the assessment schedule in [Table 8-1](#).

Two interim analyses (IA) are planned for this study:

- A **blinded IA**, after approximately 50% (275) of subjects have completed the double-blind treatment period (including early withdrawals), will be conducted to re-estimate the sample size by providing information on the variance for this trial relative to the planned assumptions to account for potential higher variability in general Asian population.

- An **unblinded IA** will be conducted after 70% (385, if no increase of sample size is needed following the blinded IA) of subjects have completed the double-blind treatment period (including early withdrawals), to determine whether the study will stop early or continue to the final primary analysis (full sample size). Study recruitment will continue until unblinded IA read-out.

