2.1.4.2 Safety endpoints

Subject Incidence

The subject incidence for a given event in a given period is defined as the number of subjects with at least one reported occurrence of the event divided by the number of subjects who entered that period. For subjects with multiple occurrences of the same event, the event will only be counted once per subject.

Exposure-Adjusted Subject Incidence Rate

The exposure-adjusted subject incidence rate for a given event in a given period is defined as the number of subjects with at least one reported occurrence of the event in a given time period divided by total subject years at risk in that period. The time at risk for each subject will differ for each adverse event. For subjects with events, only the time until the first event contributes to the total subject years at risk. For subjects who do not experience the event, the time at risk will be up to the last available visit. This rate will be presented per 100 subject years. For subjects with multiple occurrences of the same event, the event will be only counted once per subject.

Treatment-Emergent Adverse Event (TEAE)

Adverse Events (AEs) recorded on the Adverse Events eCRF page that occurs on or after first dose of investigational product and up to and including end of study.

Serious Adverse Event (SAE)

SAEs determined by the flag indicating if the adverse event is serious on the Adverse Events eCRF page will include those that occur after signing of the informed consent and up to and including end of study.

Treatment-Emergent Serious Adverse Event

A treatment-emergent serious adverse event is an SAE considered to be treatment-emergent.

Treatment-Related Adverse Event

A treatment-related AE is defined as a treatment-emergent adverse event that is considered by investigators to have reasonable possibility that it may have been caused by IP as determined by the flag indicating that there is a reasonable possibility that the AE is related to investigational product on the Adverse Events eCRF page.

Treatment-Related Serious Adverse Event

A treatment-related serious adverse event is an SAE considered to be treatment-related.

Adverse Event leading to discontinuation of study treatment

An AE leading to discontinuation of study treatment will be identified by the item “Action Taken With Study Treatment” on AE page of CRF when it’s reported as “Drug withdrawn”.

Serious Adverse Event leading to discontinuation of study treatment

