2.7.1 Adverse events (AEs)

The Medical Dictionary for Regulatory Activities (MedDRA) version 21.0 or later will be used to code all adverse events (AE) to a system organ class (SOC) and a preferred term (PT). All adverse events will be graded using the Common Terminology Criteria for Adverse Events (CTCAE) Version 4 or higher. All adverse event tables will be summarized by treatment group.

The overall subject incidence of AEs and exposure-adjusted subject incidence will be summarized for all TEAEs, AEs leading to discontinuation of study treatment, all treatment-related AEs, SAEs, SAEs leading to discontinuation of study treatment, treatment-related SAEs and deaths as defined in **Table 2-4**.

Table 2-4 AE Summaries of subject incidence and exposure-adjusted subject incidence

Category	Summary by SOC and PT	Summary by SOC, PT and maximum CTCAE grade	Summary by PT only
All TEAEs	Y	Y	Y
SAEs	Y	Y	Y
AEs leading to discontinuation of study treatment	Y		
All treatment-related AEs	Y		
SAEs leading to discontinuation of study treatment	Y		
Treatment-related SAEs	Y		
Deaths	Y		

For all AEs tables presented by SOC and PT (and grade), the SOCs will be presented in alphabetical order and PTs will be ordered within the SOC by decreasing order of frequency.

AE tables by preferred term only will be sorted in descending order of frequency.

Note, for exposure-adjusted AEs the sorting will be based on the exposure-adjusted subject incidence rate.

Subject incidence all treatment-related AEs and serious treatment-related AEs will be tabulated by SOC and PT for the DB period.

All AEs, deaths (see [Section 2.7.2](#) for details), SAEs and AEs leading to permanent study drug discontinuation will be listed separately.

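### Crude double-blind AE incidence mixes a 12-week window for open-label entrants with one of up to about 20 weeks for everyone else, so it depends on a post-randomisation event

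*SAP*

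**What the plan says.** SAP 2.1, Table 2-1 defines a double-blind phase that explicitly includes safety follow-up and gives it two end points:

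- Subjects not entering the open-label extension (OLE): "For subject who won't join in OLE: end of study date".
- Subjects entering it: "For subject who join in OLE: the End of Treatment visit in DB period".

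Protocol section 3 sets how long the first group is followed. Completers who do not enter OLE have a safety visit 8 weeks after Week 12. Subjects who stop treatment and do not stay for scheduled visits "will have the safety follow-up visit 12 weeks after the last dose". Those who stop but stay for visits are also seen at Week 20.

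SAP 2.1.4.2 defines crude subject incidence as "the number of subjects with at least one reported occurrence of the event divided by the number of subjects who entered that period", with no time element. SAP 2.7.1 plans two measures side by side: "The overall subject incidence of AEs and exposure-adjusted subject incidence will be summarized for all TEAEs" and for the other categories in Table 2-4. In the exposure-adjusted rate, subjects with an event contribute time to the first one; otherwise, "For subjects who do not experience the event, the time at risk will be up to the last available visit".

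Protocol 5.3 makes OLE entry depend on completing double-blind treatment on study drug, on consent, on having no local access to launched erenumab, and on not having developed a contraindication or a significant medical, laboratory or ECG finding during the double-blind period. No visible text plans an AE table restricted to a common 12-week window.

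**The concern.** A crude percentage compares arms fairly only if subjects in both arms are watched for equally long. Here a completer outside OLE is watched for 8 weeks longer than one who enters it. What decides the window is known only after randomisation, and treatment can plausibly influence it through tolerability and response. It can even depend on the safety outcome: a finding that bars OLE entry gives that subject the longer window.

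Two consequences follow. Both arms' percentages rise above the 12-week risk by an amount that depends on uptake. If uptake differs by arm, the difference between the percentages also moves, and could suggest a difference that is not there or hide one that is. Adverse events are a secondary endpoint, AE tables go to the DMC at the unblinded interim (SAP 2.12.2), and the interim CSR is intended for regulatory submission (SAP 2.1).

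**Working it through.** **Windows from the documents.** Completer outside OLE: Week 12 + 8 weeks = Week 20 = Day 140, the day given in Protocol Table 8-1. The other route agrees: last double-blind dose at Week 8 + 12 weeks = Week 20. OLE entrant: Week 12 = Day 84. The ratio is 20/12 = 1.67, so 67% longer. Discontinuers who do not return are seen at Week 12, 16 or 20 if the last dose was at Day 1, Week 4 or Week 8.

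**Assumptions.** The documents give neither AE risk nor OLE uptake by arm. I assume the same exponential time to first AE in both arms, a 12-week risk p12 of 5% to 40%, uptake u of 70% to 95%, and 20 weeks for every non-entrant.

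**Formulas.** Weekly hazard h = -ln(1 - p12)/12. Twenty-week risk p20 = 1 - exp(-20h). Crude rate in an arm = u·p12 + (1 - u)·p20. Gap between arms = (difference in u) × (p20 - p12), so equal uptake gives a gap of exactly zero.

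**Base case, p12 = 35%.** h = -ln(0.65)/12 = 0.0359; p20 = 51.2%; p20 - p12 = 16.2 points.

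- Uptake 90% vs 80%: 0.9 × 35 + 0.1 × 51.2 = 36.6% against 0.8 × 35 + 0.2 × 51.2 = 38.2%. Gap 1.6 points.
- Uptake 95% vs 75%: 35.8% against 39.1%. Gap 0.20 × 16.2 = 3.2 points.

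**Range of risks, uptake 90% vs 70%.**

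| p12 | p20 | Crude rates | Gap (points) |
|---|---|---|---|
| 5% | 8.2% | 5.3% vs 6.0% | 0.6 |
| 20% | 31.1% | 21.1% vs 23.3% | 2.2 |
| 40% | 57.3% | 41.7% vs 45.2% | 3.5 |

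Equal uptake moves the level only: at p12 = 20%, both arms read 21.1% with 90% uptake and 25.5% with 50%.

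**Does exposure adjustment repair it?** Take p12 = 20%, uptake 90% vs 70%, and let the hazard after Week 12 change. Rates are per 100 subject-years.

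| Hazard after Week 12 | Crude rates | Exposure-adjusted rates |
|---|---|---|
| Unchanged | 21.1% vs 23.3% | 96.7 vs 96.7 |
| Halved | 20.6% vs 21.7% | 94.1 vs 89.6 |
| Zero | 20.0% vs 20.0% | 91.3 vs 82.1 |

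The two measures fail under opposite conditions and in opposite directions. The arm with lower uptake looks worse on the crude rate and better on the exposure-adjusted rate. Between the extremes, both are off.

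**With a common Week 12 cut.** Crude incidence is p12 in both arms, so equal hazards and complete follow-up to Week 12 give a gap of 0.0 points whatever the uptake.

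**The case against.** The case for leaving the plan alone is substantial. Exposure-adjusted incidence is already planned for every AE category, and under the constant hazard used for the headline figures it is identical in the two arms. If risk instead falls off drug, the crude gap itself shrinks. SAP 2.7 rules out between-arm testing of safety data. With about 275 per arm and rates near 37%, the standard error of a difference is √(2 × 0.37 × 0.63/275) = 4.1 points, so a 1.6-point artefact is under half a standard error.

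The illustration also leans high. Some discontinuers have windows shorter than 20 weeks, and a data cut-off can catch non-entrants before their safety visit. Text is blacked out just after the Table 2-1 footnote and in the safety sections, and the table shells are not public, so a further rule cannot be excluded. Ending the entrants' window at End of Treatment is sensible in itself, because all of them then receive erenumab.

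These points limit the size and importance of the problem. They do not remove it: the crude percentages are still planned, will be read as they stand, and have no visible common cut. Exposure adjustment answers the point only under a constant hazard, which is doubtful for Weeks 12 to 20, since these fall 4 to 12 weeks after the last planned dose.

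A reader might go further and infer that the AE comparison will be biased between arms. The documents do not support that. It needs uptake to differ by arm, and no uptake figure is given. All subjects who complete on study drug are invited, both arms are blinded when they choose, and both are offered erenumab. Differential entry is plausible, not shown.

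**Conclusion.** The point holds as a minor one. As written, crude AE incidence by arm mixes windows of 12 weeks and up to about 20 weeks, and the mix is set after randomisation. The spurious difference is zero if uptake is equal. On the assumptions shown it is 1.6 to 3.2 points for uptake gaps of 10 to 20 points at a 12-week risk of 35%, and 0.6 to 3.5 points across risks of 5% to 40% at 90% vs 70% uptake. These are upper-end values, resting on a constant hazard and a full 20 weeks for every non-entrant. No hypothesis test, and no efficacy result, is affected. It would be too much to say that the planned exposure-adjusted tables leave the matter unaddressed, and also too much to say that they settle it.

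**What to change.** In SAP 2.1 and 2.7.1, base the between-arm crude AE tables on one window for all dosed subjects: first double-blind dose to the Week 12 visit, or Day 84 where there is no such visit, whether or not treatment was stopped early. Tabulate later safety follow-up events separately. Keep the exposure-adjusted tables.

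Do not truncate at a fixed time after the last dose. A rule of last dose plus 28 days, for example, would give about 4 weeks to a subject dosed only at Day 1, about 8 to one whose last dose was at Week 4, and 12 to a completer. Window length would again follow a post-randomisation event, this time discontinuation.

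The cost is one window flag in the safety programs and a few extra tables. No new data are needed, because AE collection already runs to 12 weeks after the last dose and so nominally reaches Week 12 even for a subject dosed only once. The downside is that events after Week 12 appear in their own table and not in the main one.
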